## Appendix 6 Best-Corrected Visual Acuity Testing

#### **SCOPE**

Best-corrected visual acuity (BCVA) will be measured by trained and certified personnel at the study sites.

The Sponsor recognizes that it may be difficult to fully mask site staff in an open label surgical study.

The Sponsor will require that the following steps be implemented as a best attempt to mask VA examiners in order to minimize biases in VA assessments.

- The VA examiner will only conduct refraction and VA assessments and will be masked as best as possible to patient study eye assignment, study visit type, and patient treatment assignment.
- The VA examiner will have no access to a patient's BCVA scores from previous visits and will be aware only of the patient's refraction data from previous visits.
- The VA examiner may provide no other direct or indirect patient care.
- Patients and unmasked site personnel will be asked not to discuss the study eye assignment, study visit type, and patient treatment assignment with the VA examiner.

VA will be measured at the intervals specified in the protocol (see Section 4.5.5, Appendix 1, and Appendix 2).

#### EQUIPMENT

The following is needed at minimum to conduct the examination:

- Examination lane of adequate dimensions to allow testing at required distances
- Standard chair with a firm back
- Set of three Precision Vision™ or Lighthouse distance acuity charts (modified ETDRS Charts 1, 2, and R)
- Retro-illuminated box
- Trial frame
- Trial lens set

#### TRAINING AND CERTIFICATION

A VA specifications document, procedure manual, and training materials will be provided to the investigational sites, and VA examiner certification will be obtained. The VA examination room also must be certified before any VA examinations are performed. If new VA personnel or VA rooms are added to the study, certification must be obtained prior to performing study assessments.

# Appendix 7 Grading Scales for Anterior Chamber Flare or Cells and Vitreous Cells

## **GRADING SCALE FOR ANTERIOR CHAMBER FLARE OR CELLS**

Flare	
0	No protein is visible in the anterior chamber when viewed by an experienced observer using slitlamp biomicroscopy; a small, bright, focal slit-beam of white light; and high magnification.
Trace	Trace amount of protein is detectable in the anterior chamber: This protein is visible only with careful scrutiny by an experienced observer using slitlamp biomicroscopy; a small, bright, focal slit-beam of white light; and high magnification.
1+	Slight amount of protein is detectable in the anterior chamber: The presence of protein in the anterior chamber is immediately apparent to an experienced observer using slitlamp biomicroscopy and high magnification, but such protein is detected only with careful observation with the naked eye and a small, bright, focal slit-beam of white light.
2–3+	Moderate amount of protein is detectable in the anterior chamber. These grades are similar to $1+$ but the opacity would be readily visible to the naked eye of an observer using any source of a focused beam of white light. This is a continuum of moderate opacification, with $2+$ being less apparent than $3+$ .
4+	A large amount of protein is detectable in the anterior chamber. This grade is similar to $3+$ , but the density of the protein approaches that of the lens. Additionally, frank fibrin deposition is frequently seen in acute circumstances. It should be noted that because fibrin may persist for a period of time after partial or complete restoration of the blood–aqueous humor barrier, it is possible to have resorbing fibrin present with lower numeric assignations for flare (e.g., $1+$ flare with fibrin).
Cells	
0	No cells are seen in any optical section when a large slitlamp beam is swept across the anterior chamber.
Trace	Few (1–3) cells are observed when the slitlamp beam is swept across the anterior chamber. When the instrument is held stationary, not every optical section contains circulating cells.
1+	3–10 cells/optical section are seen when the slitlamp beam is swept across the anterior chamber. When the instrument is held stationary, every optical section contains circulating cells.
2+	10–25 cells are seen when the slitlamp beam is swept across the anterior chamber. When the instrument is held stationary, every optical section contains circulating cells.

Modified from: Hogan MJ, Kimura SJ, Thygeson P. Signs and symptoms of uveitis. I. Anterior uveitis. Am J Ophthalmol 1959;47(Part 2):155–70.

## Appendix 7 Grading Scales for Anterior Chamber Flare or Cells and Vitreous Cells (cont.)

#### **GRADING SCALE FOR ANTERIOR CHAMBER FLARE OR CELLS**

#### Cells (cont.)

3+	25–50 cells are seen when the slitlamp beam is swept across the anterior
	chamber. When the instrument is held stationary, every optical section contains
	circulating cells. Keratic precipitates or cellular deposits on the anterior lens
	capsule may be present.

4+ More than 50 cells are seen when the slitlamp beam is swept across the anterior chamber. When the instrument is held stationary, every optical section contains cells, or hypopyon is noted. As for fibrin deposition, hypopyon may persist for some period of time after the active exudation of cells into the anterior chamber has diminished or ceased entirely, making it possible to have 1+ circulating cells in the anterior chamber with a resolving hypopyon.

Modified from: Hogan MJ, Kimura SJ, Thygeson P. Signs and symptoms of uveitis. I. Anterior uveitis. Am J Ophthalmol 1959;47(Part 2):155–70.

#### **GRADING SCALE FOR VITREOUS CELLS**

Number of Cells in Retro Illuminated Field	Description	Grade
0	Clear	0
1–20	Few opacities	Trace
21–50	Scattered opacities	1
51–100	Moderate opacities	2
101–250	Many opacities	3
>251	Dense opacities	4

Modified from: Nussenblatt RB, Whitcup SM, Palestine AG. Uveitis: fundamentals and clinical practice. 2nd rev. ed. St. Louis: Mosby, 1996, p. 64.

# Appendix 8 Grading Scales for Vitreous Hemorrhage

## **GRADING SCALE FOR VITREOUS HEMORRHAGE DENSITY**

Grade	Description		
None (0)	Retina is visible.		
Trace	Retina is visible and red blood cells are visible only on slitlamp examination.		
1+	Retinal detail is visible; some hemorrhage is visible by ophthalmoscopy		
2+	Large retinal vessels are visible, but central retinal detail is not visible by ophthalmoscopy.		
3+	Red reflex is visible, but no central retinal detail is seen posterior to the equator by ophthalmoscopy.		
4+	No red reflex by ophthalmoscopy.		

## VITREOUS HEMORRHAGE FUNCTIONAL GRADING SCALE

Grade	Description		
1	$\leq$ 15 letter BCVA loss from the previous visit		
2	16–30 letter BCVA loss from the previous visit		
3	>30 letter BCVA loss from the previous visit to hand motion		
4	Light Perception or worse		

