## 5.1.5.4 Recommended Management of Cases of Vitreous Hemorrhage

*The recommended management of patients with* vitreous hemorrhage secondary to implant-related procedures throughout the study *is presented* in Table 5.

Timing	Patient's Examination and Management Guidelines
Day of vitreous hemorrhage diagnosis	• If the diagnosis of vitreous hemorrhage is made during a scheduled visit and the view of the vitreous cavity is limited , perform ocular B-scan ultrasonography if possible in addition to the assessments scheduled for that specific visit.
	• If the diagnosis of vitreous hemorrhage is made during an unscheduled visit and the view of the vitreous cavity is limited , perform ocular B-scan ultrasonography if possible in addition to the assessments listed in Appendix 4.
	• A safety assessment visit (scheduled or unscheduled) should be performed approximately 2 weeks after occurrence of vitreous hemorrhage (see Appendix 4). If possible, perform ocular B-scan ultrasonography if the view of the vitreous cavity is limited.
Approximately 4 weeks after occurrence (scheduled visit)	• If possible, perform ocular B-scan ultrasonography if the view of the vitreous cavity is limited, in addition to the assessments scheduled for that specific visit.
	
 
An unscheduled safety assessment visit should be performed between 4 and 8 weeks after occurrence of vitreous hemorrhage (Appendix 4).
 

Approximately 8 weeks after occurrence (scheduled visit)	• If possible, perform ocular B-scan ultrasonography if the view of the vitreous cavity is limited.
	
 
If vitreous hemorrhage causes loss in BCVA and neither assessment of the macula nor SD-OCT can be performed successfully:
 

	
 
Discuss a pars plana vitrectomy with the patient as a possibility to remove the vitreous hemorrhage. Consultation with the Medical Monitor is advised prior to performing pars plana vitrectomy.
 

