#### 5.2.3 Adverse Events of Special Interest (Immediately Reportable to the Sponsor)

Adverse events of special interest are required to be reported by the investigator to the Sponsor immediately (i.e., no more than 24 hours after learning of the event; see Section 5.4.2 for reporting instructions). Adverse events of special interest for this study are as follows:

- Cases of potential drug-induced liver injury that include an elevated ALT or AST in combination with either an elevated bilirubin or clinical jaundice, as defined by Hy's Law (see Section 5.3.5.6)
- Suspected transmission of an infectious agent by the study drug, as defined below

Any organism, virus, or infectious particle (e.g., prion protein transmitting transmissible spongiform encephalopathy), pathogenic or non-pathogenic, is considered an infectious agent. A transmission of an infectious agent may be suspected from clinical symptoms or laboratory findings that indicate an infection in a patient exposed to a medicinal product. This term applies only when a contamination of the study drug is suspected.

- Sight-threatening adverse events: an adverse event is considered to be sight threatening if it is a serious adverse event (as defined in Section 5.2.2) and it meets one or more of the following criteria:
  - The adverse event causes a decrease of ≥30 letters in BCVA (compared with the last assessment of VA prior to the most recent treatment) lasting more than 1 hour.

- The adverse event requires surgical intervention (i.e., conventional surgery, vitrectomy, vitreous tap, or biopsy with intravitreal injection of anti-infective medications, or laser or retinal cryopexy with gas) to prevent permanent loss of sight.
- The adverse event is associated with severe intraocular inflammation (e.g., endophthalmitis, 4+ anterior chamber cell/flare or 4+ cells in the vitreous; see Appendix 7 for intraocular inflammation grading scales).

Note: Adverse events should be reported, listing the underlying cause (if known) of the event as the primary event term (see Section 5.3.5.2).

- Ocular adverse events of special interest, defined as any of the events listed below, regardless of whether they occur in the study eye or the fellow eye, in a patient randomized to the PDS arm or the intravitreal arm, or the AE causality:
  - Vitreous hemorrhage
  - Endophthalmitis
  - Retinal detachment
  - Conjunctival retraction
  - Conjunctival erosion

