- MedDRA Query (SMQ) (Narrow), ischaemic cerebrovascular conditions SMQ (Narrow), and haemorrhagic cerebrovascular conditions SMQ (Narrow) or
- non-fatal myocardial infarction AEs defined by terms from the myocardial infarction SMQ (Narrow) or
- vascular death (including deaths of unknown cause)

Of note, vitreous hemorrhage data will be presented by the functional grading scale for vitreous hemorrhage (see Study GR40458 Study Protocol Appendix 8) which incorporates impact of vitreous hemorrhage on patient's BCVA. All vitreous hemorrhage data will be presented however for key analyses the focus will be on Grades 3 and 4 as these are clinically relevant when discussing vitreous hemorrhage.

A subgroup analysis of cataract incidence will be performed by baseline lens status subgroup (phakic vs pseudophakic), as in the Primary CSR Section 3.11.8.

In addition, the rates of intraocular inflammation AEs will be analyzed as in the Primary CSR Section 6.3.5.2.1, based on selected PTs according to the Standardization of Uveitis Nomenclature (SUN) (Jabs et al. 2005). Intraocular inflammation will be defined as anterior uveitis (included iritis, iridocycltis, anterior cyclytis, anterior channel cell, flare, and inflammation); intermediate uveitis (included pars planitis, posterior cyclitis, hyalitis, vitritis, and vitreous haze); posterior uveitis (included choroiditis, chorioretinitis, retinochoroiditis, retinitis, neuroretinitis, and retinal vasculitis); and events which were not otherwise specified (included eye inflammation, uveitis, post procedural inflammation, incision site inflammation, inflammation of wound, and ocular vasculitis). Endophthalmitis, while included in the SUN criteria for intraocular inflammation, will be analyzed separately as an AESI.

Adverse events (AEs) of endophthalmitis will additionally be summarized as incidence rates by treatment group on a per study treatment intervention basis (total number of endophthalmitis AEs divided by the total number of interventions in the study eye. Interventions in the intravitreal group include intravitreal ranibizumab injections. Interventions in the PDS 100 mg/ml group include implantation, PDS refill-exchange procedure, and supplementary ranibizumab treatment in the study eye.

Frequency tables including patient incidence rates will also be generated by treatment group and by onset of events using the following time windows relative to first dose or implant surgery:

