# 4.7.5 Ocular Assessments

Results of the following ocular assessments will be summarized by treatment group, by timepoint and by eye (study vs. non-study) as applicable, using descriptive summaries:

- intraocular pressure (IOP)
- slit lamp examination
- indirect ophthalmoscopy

Changes from baseline for IOP assessments will be tabulated. The presence of intraocular inflammation and vitreous hemorrhage, as determined on slit lamp examination, will be tabulated by grade (according to grading scales for flares and cells in Study GR40548 Protocol Appendix 7, and vitreous hemorrhage density and functional scales in Study GR40548 Protocol Appendix 8). The presence of retinal break or detachment as determined from ophthalmoscopy will be tabulated.

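### The vitreous hemorrhage functional grade counts letters lost since the previous visit, so stepwise losses above 30 letters can miss Grade 3 and an unchanged Grade 3 eye reads as Grade 1 at later visits

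*Protocol*

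**What the plan says.** Protocol Appendix 8 gives two scales for vitreous hemorrhage. On the functional scale, Grade 1 is a loss of at most 15 letters since the previous visit, Grade 2 is "16–30 letter BCVA loss from the previous visit", and Grade 3 is ">30 letter BCVA loss from the previous visit to hand motion". Grade 4 is "Light Perception or worse", which needs no reference visit. The density scale records what can be seen in the eye on the day and also has no reference visit.

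SAP 4.7.1 (Adverse Events) presents vitreous hemorrhage on the functional scale and undertakes to show all the data, but adds: "for key analyses the focus will be on Grades 3 and 4 as these are clinically relevant when discussing vitreous hemorrhage". SAP 4.7.5 (Ocular Assessments) tabulates hemorrhage by grade using the "vitreous hemorrhage density and functional scales in Study GR40548 Protocol Appendix 8", within a set of assessments summarized by treatment group, timepoint and eye.

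Neither document says which visit's grade stands for the event (onset, worst or last), or whether the previous visit means the last one before onset. Protocol 5.3.5.3 keeps the most extreme severity of a persistent adverse event, but that concerns adverse event severity, not this scale.

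The BCVA schedule also matters. The implant arm has BCVA at Days 2 and 7 (Appendix 1, Table 1). The intravitreal arm's first scheduled BCVA after randomization is Week 4 (Appendix 2, Table 1). For procedure-related hemorrhage, Protocol 5.1.5.4, Table 5 adds visits: "A safety assessment visit (scheduled or unscheduled) should be performed approximately 2 weeks after occurrence of vitreous hemorrhage", and another between 4 and 8 weeks. Appendix 4 requires BCVA at unscheduled visits.

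**The concern.** A reference that moves with every visit measures the size of an event correctly only when the whole loss falls between one unaffected visit and the next. If vision falls over several visits, each visit sees only its own share. If vision falls once and stays down, later visits see no loss.

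Vitreous hemorrhage is a named risk of the implant and its procedures (Protocol 5.1.3.1) and an ocular adverse event of special interest (Protocol 5.2.3). The SAP treats Grades 3 and 4 as the clinically relevant ones. An event that cost well over 30 letters but never shows more than 30 between adjacent visits falls outside that group. In the by-visit table, a patient with no improvement in acuity moves from Grade 3 to Grade 1, which a reader would take as recovery.

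**Working it through.** **Inputs.** The cut-points are those of the Appendix 8 functional scale: at most 15 letters, 16–30, and more than 30. The documents state no figure to reproduce. The acuity courses below are illustrative assumptions.

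**Formulas.**
- As written: loss at visit *k* = BCVA at visit *k*−1 minus BCVA at visit *k*.
- Fixed reference: loss at visit *k* = last BCVA before onset minus BCVA at visit *k*.

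The first value in each course is the last BCVA before onset.

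| Course (letters) | Loss since previous visit | Grade as written (worst) | Loss since before onset | Grade, fixed reference (worst) |
|---|---|---|---|---|
| 75, 50, 22 | 25, 28 | 2, 2 (2) | 25, 53 | 2, 3 (3) |
| 74, 54, 34, 34 | 20, 20, 0 | 2, 2, 1 (2) | 20, 40, 40 | 2, 3, 3 (3) |
| 74, 44, 14, 14 | 30, 30, 0 | 2, 2, 1 (2) | 30, 60, 60 | 2, 3, 3 (3) |
| 74, 59, 44, 29 | 15, 15, 15 | 1, 1, 1 (1) | 15, 30, 45 | 1, 2, 3 (3) |
| 74, 34, 34, 34 | 40, 0, 0 | 3, 1, 1 (3) | 40, 40, 40 | 3, 3, 3 (3) |

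**Stepwise loss (first four rows).** The largest total that stays at Grade 2 over two visits is 30 + 30 = 60 letters. The largest that stays at Grade 1 over three visits is 15 + 15 + 15 = 45. Taking the worst grade does not help, because no single visit reaches Grade 3.

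**Sudden, persistent loss (last row).** The onset visit is Grade 3 under either reference, so the worst grade is 3 either way. Only the later visits differ: Grade 1 as written, Grade 3 with the fixed reference.

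**Visit schedule.**
- A 40-letter loss by Week 4, seen at Day 2, Day 7 and Week 4 as 74, 64, 44, 34, has steps of 10, 20 and 10 and grades of 1, 2 and 1. The same loss seen only at Week 4 (74, 34) is 40 letters, Grade 3.
- The opposite also occurs. A fall from 74 to 34 at Day 2 that returns to 74 by Week 4 is Grade 3 at Day 2 (74 − 34 = 40). With no BCVA before Week 4, the measured loss is 74 − 74 = 0.

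Extra early visits can therefore lower or raise the recorded worst grade.

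**The case against.** The strongest reply is that the documents never say an event is re-graded at every visit. The Grade 3–4 focus sits in the adverse event section, where the unit is the event. If the previous visit is read as the last one before onset, both problems disappear. That reading is possible, but it is not written down, and SAP 4.7.5 puts the same scale into a by-timepoint tabulation, where the literal reading is the natural one.

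The safeguards are real:
- All hemorrhages are presented, and each is an event of special interest whatever its grade.
- The density scale continues to show blood that has not cleared, and change in BCVA over time is reported.
- A serious event with a loss of at least 30 letters "compared with the last assessment of VA prior to the most recent treatment", lasting more than one hour, meets the sight-threatening definition in Protocol 5.2.3. That is a separate definition linked to seriousness. It uses a different reference and partly backs up the functional grade.
- The Grade 3–4 focus is descriptive, and no hypothesis test depends on it.

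These points limit the consequence but do not restore the functional grade of a stepwise event.

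Three stronger inferences are tempting but unsupported:
- **Persistent Grade 3 events drop out of the event count.** They do so only if something other than the worst grade is used, which the documents leave open.
- **The implant arm is systematically graded milder.** Days 2 and 7 can split a loss, but they can also catch a transient one that a Week 4 visit would miss.
- **Following Table 5 lowers the grade.** Its added visits begin about two weeks after occurrence. They cannot lower a grade already recorded; they affect only later-visit grades or a loss that continues in steps.

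**Conclusion.** The point holds in a limited form. Read literally, the functional scale under-grades hemorrhages whose loss accrues in steps: up to 60 letters over two visits without Grade 3, whichever visit's grade is used. It also shows an unchanged Grade 3 eye with measurable letters as Grade 1 at later visits. The text does not settle whether persistent hand-motion vision stays Grade 3.

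The effect is limited to the key-analysis focus in SAP 4.7.1 and the functional part of the by-visit table in SAP 4.7.5. Grade 4, the density scale and the reporting of every hemorrhage are untouched.

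The conclusion rests on the literal reading of the reference visit and on illustrative courses. The documents give no frequency of stepwise loss, so the number of affected patients is unknown. Step-splitting is possible in the implant arm because of its extra visits, but the net direction of any between-arm effect cannot be determined from the documents.

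**What to change.** 1. **SAP 4.7.1:** derive each event's functional grade from the worst BCVA between onset and resolution, compared with the last BCVA before onset. Keep Grade 4 as defined.
2. **SAP 4.7.5:** hold that same pre-onset reference at every visit of the event.
3. **Both sections:** show the Appendix 8 previous-visit grade alongside, and label the new derivation as added after the Primary and Update CSRs, which were complete when SAP Version 3 was written.

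Do not substitute the randomization-visit value for every event before Week 4. For a hemorrhage starting after Day 2, that would count any post-surgical acuity loss already present at Day 2 as hemorrhage loss, in the implant arm only. The last BCVA before onset is the consistent reference.

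The cost is a small amount of SAP wording and a re-derivation from BCVA values and adverse event dates already collected. Some events may move up to Grade 3, and the table will differ from the earlier CSRs; the side-by-side display makes that difference traceable.

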## Appendix 9 Fundus Autofluorescence

### **SCOPE**

Fundus autofluorescence (FAF) will be performed at the study sites by trained personnel who are certified by the central reading center. FAF imaging will be performed for each patient at the intervals specified in the protocol (see Section 4.5.6, Appendix 1, and Appendix 2) and will be forwarded to the central reading center for analysis and/or storage. Analysis (if applicable) of FAF images will be performed by the central reading center. The list of timepoints at which images will be analyzed are recorded in the reading center manual.

#### **EQUIPMENT**

Equipment utilized during this trial is described in the central reading center manual. The ability to transfer images to electronically export digital files is required (i.e., no printed FAF images will be sent to the central reading center).

## **PROCEDURES AND CERTIFICATION**

The central reading center will provide the study manual and training materials. FAF operators, systems, and software will be certified prior to any evaluation of patients.

